21.1.3.2 Persistence

Having established which repellent products are effective at which doses, the persistence of all repellent products at doses achieving at least 30 % protection (at time zero) will be determined. Persistence will be determined using an extended version of the protocol described in 21.1.3.1. Preparation, and control testing, will be conducted in the same manner, then the repellent products at the appropriate dose will be applied and tested for ten minutes as previously, and the observation will be repeated every hour for six hours (Figure 5). After testing, the participant will be given access to washing facilities to wash off the topical repellent. This data will allow calculation of the Median Protection Time/Effective Dose (ET_{50} and ED_{50}). To determine the Median Complete Protection time (mCPT), the same protocol will be used however the first test sampling period will be extended until the first fly-arm contact.

[figure not shown]

Figure 5. Timescale for repellency complete protection time (CPT), and median protection time, testing in the laboratory.

21.1.4 Wearable repellent devices

The protection afforded by wearable repellent devices against *M. sorbens* contacts, formulated at the effective dose determined in 21.1.3.1, will be measured (protective efficacy) and the persistence of this effect determined. Wearable repellent devices will be tested in an extended version of the protocol described in 21.1.3.2. Preparation and control testing will be conducted in the same manner but without the application of any diluent prior to the control test. The participant will then be given the wearable repellent device and asked to put it on (i.e. wear the necklace or neckband around their wrist), and a ten-minute test period will be conducted as previously described (21.1.3.1). After this, the observation will be repeated every hour for six hours. These procedures (control then tests over six hours) will be repeated every week for four weeks, and each timepoint participants will wear the repellent devices that they wore in the initial test at the first timepoint (Figure 6).

[figure not shown]

Figure 6. Timescale for wearable repellent device testing in the laboratory.

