16.1.2 Wearable repellent devices

One or more of five insect repellent products, with the possible addition of vanillin (Table 2), previously determined by laboratory experiments at LSHTM to exhibit potential repellency to *Musca sorbens*, and formulated into long-lasting plastic formulations made of low-density polyethylene (LDPE) or high-density polyethylene (HDPE). In the case of permethrin, the wearable repellent technology will be permethrin-treated fabric, e.g. a permethrin treated neckband. PMD will be allowed in a wearable repellent device, but not as a topical product, because of safety advice against its use on children's faces (57). Vanillin is an organic compound that it is thought may enhance the protection time of insect repellents.

Table 2. Insect repellent products that will be formulated into long-lasting plastic formulations will be selected from these five actives

Generic name	Repellent active ingredient*	CAS number	Manufacturer
DEET	N,N -Diethyl-meta-toluamide	134-62-3	Merck ⁽¹⁾
Oil of Lemon Eucalyptus, PMD	para-Mentane-3,8-diol OR Citriodiol® (64% PMD [a mixture of the cis and trans isomers of p-mentane-3,8-diol) together with a number of minor constituents found in essential oil which enhance the efficacy further])	42822-86-6	Merck ⁽²⁾ Citrefine ⁽³⁾
IR3535	3-[N-butyl-N-acetyl]-aminopropionic acid ethyl ester	52304-36-6	Merck ⁽⁴⁾
Picaridin	2-(2-hydroxyethyl)-1-piperidinecarboxylic acid 1-methylpropyl ester	119515-38-7	Alfa chemistry ⁽⁵⁾
Permethrin	(m-Phenoxybenzyl)-cis,trans-3-(2,2-dichlorovinyl)-2,2-dimethylcyclopropanecarboxylate	52645-53-1	Merck ⁽⁶⁾ OR Fagron Hellas ⁽⁷⁾

*Vanillin (4-Hydroxy-3-methoxybenzaldehyde, CAS number 121-33-5, available from Merck) may be used as a synergist with these repellent actives (<https://origin-webqws.sial.com/catalog/product/sial/v1104?lang=en®ion=GB>)

⁽¹⁾ <https://www.sigmaaldrich.com/catalog/substance/deet1912713462311?lang=en®ion=GB>

⁽²⁾ <https://origin-webqws.sial.com/catalog/product/aldrich/r751898?lang=en®ion=GB>

⁽³⁾ <https://www.citrefine.com/citriodiol/#what-is-citriodiol>

⁽⁴⁾ https://origin-webqws.sial.com/catalog/product/sial/34524?lang=en®ion=GB&cm_sp=Insite--recent_fixed--recent5-3

⁽⁵⁾ <https://www.alfa-chemistry.com/sec-butyl-2-2-hydroxyethyl-piperidine-1-carboxylate-cas-119515-38-7-item-289774.htm>

⁽⁶⁾ <https://origin-webqws.sial.com/catalog/product/sial/45614?lang=en®ion=GB>

⁽⁷⁾ <https://gr.fagron.com/en-gr>

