21.1.3 Topical repellents

21.1.3.1 Protective Efficacy

Consenting participants will be asked to avoid the use of fragranced cosmetic or washing products for 12 hours prior to each laboratory trial. Immediately before testing, the participant's arm will be washed with unscented soap, rinsed with water, rinsed with 70 % ethanol in water, and towel dried. An analytical standard of the repellent will be tested at five incrementally increasing doses up to a maximum of 20 %, each diluted in ethanol.

For the first test, the diluent alone (1.4 ml) will be tested as a control. This will be applied to the participant's arm and allowed to dry for one minute. The participant will then insert his/her arm into a purpose-designed insect cage, with a hole in the top allowing a camera lens to film the upper surface of the hand and arm. The cage will contain 100 test insects, and insect behaviour on the arm will then be filmed for ten minutes. This video footage will retrospectively be analysed for the number of fly contact, and the total duration of fly contact. The participant will be instructed to refrain from moving his/her arm, which will disturb landing flies.

For the test to proceed, there must be five or more fly contacts, with the diluent (control,) in the ten-minute observation period. After this, the participant will remove their arm from the cage, carefully brushing off any flies as they leave. The lowest dose of repellent in ethanol (1.4 ml) will then be applied to the arm and allowed to dry for one minute. The participant will then re-insert his/her arm into the cage with the test insects, and insect behaviour on the arm will again be filmed for ten minutes.

This procedure will be repeated for each incremental dose of the repellent, up to a maximum of 20 % active ingredient. Each dose will be tested serially and without delay. To determine the repellent dose, the doses applied to reach that which was effectively repellent will be summed. If at any point the fly-arm contact rate drops below five in 10 minutes, the test will be stopped. After all repellent doses have been tested, 1.4 ml of the diluent control will be applied to the participant's other arm, and tested again as per the first ten-minute test, in order to verify continued fly contact/landings. If at this point there are less than five fly contacts, the results of the experiment will be discarded.

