22.2.5 Permethrin

Permethrin, a member of the pyrethroid class of insecticides (75), is classed as a repellent when used to pre-treat clothing, and is the only insect repellent that is currently used for factory treatment of clothing (76). As with PMD, in this study Permethrin will only be considered for use in the wearable repellent devices.

In 2009, the US EPA evaluated multiple scenarios for permethrin factory-treated clothing, including toddlers wearing or mouthing the clothing, and found the product unlikely to pose any

significant immediate or long-term hazard to those wearing the clothing (76). Multiple studies have demonstrated that maximum permethrin uptake from impregnated clothing is five times lower than the regulations established by the WHO and US EPA, and therefore have concluded that health impairments are unlikely (77–79). This study will focus on the use of polymer coated fabric, which has the lowest skin absorption rate when compared to other types of treated clothing (39). The majority of studies also show that impregnated clothing is usually comfortable, non-irritating and non-odorous (37).

When used at appropriate concentrations, insecticide-treated clothing is deemed safe. For example, one study showed that permethrin is transferred from clothing to skin at a rate of 0.49 % per day from fabric treated with permethrin at a rate of 0.125 mg/cm². This equated to 0.00006 mg/kg bw/day, with the permethrin AEL_{medium term} (Acceptable exposure level for medium term use) 0.05 mg/kg bw/day (80). For the material safety data sheet (MSDS) see Appendix 14.

In summary, the amount of permethrin that is allowed in treated fabric is low, and from the fabric it is thought to be poorly absorbed through the skin.

The following international agencies recommend insecticide treated apparel:

- The U.S. Centre for Disease Control and Prevention (CDC)
- The World Health Organization (WHO)
- National Institute for Occupational Health and Safety
- The American Academy of Family Physicians
- The Public Health Agency of Canada

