26.3 Data analysis

26.3.1 Protective Efficacy, p

The protection (protective efficacy, p) afforded by a repellent product will be presented as a percentage. p will be estimated by comparing fly-arm contact duration and fly-eye contact frequency, in laboratory and field trials respectively, after application (or wearing) of the repellent product to that during the control period.

Equation 1. Protective Efficacy, p

$$p = 100 \times ((C - T)/C)$$

Where (laboratory trials):

- C is the total duration of fly-arm contact before application of repellent ('control' measure), and
- T is the total duration of fly-arm contact after application of repellent ('treatment' measure)

Where (field trials):

- C is the frequency of fly-eye contacts before application of repellent ('control' measure), and

- T is the frequency of fly-eye contacts after application of repellent ('treatment' measure)

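### Laboratory device tests score flies disabled by permethrin as repelled, which can inflate the later hourly protective efficacy and ET50

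*Combined protocol and SAP*

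**What the plan says.** Protocol 22.2.5 states: "Permethrin, a member of the pyrethroid class of insecticides (75), is classed as a repellent when used to pre-treat clothing". Section 16.1.2 fixes the format: "In the case of permethrin, the wearable repellent technology will be permethrin-treated fabric, e.g. a permethrin treated neckband". Permethrin is not among the topical actives in Table 1, so within the laboratory clinical trial the device test is its only measurement of PE.

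Section 21.1.4 builds the device test on the topical arm-in-cage procedure, with the device worn round the wrist. On the cage, 21.1.3.1 says: "The cage will contain 100 test insects, and insect behaviour on the arm will then be filmed for ten minutes". After the control reading the participant is to "re-insert his/her arm into the cage with the test insects". For devices there is a control, a first test reading, and then: "After this, the observation will be repeated every hour for six hours". The whole sequence, with a new control, is repeated weekly for four weeks.

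Equation 1 (26.3.1) is p = 100 × (C − T)/C. For the laboratory, "T is the total duration of fly-arm contact after application of repellent"; C is the same quantity before application. Neither term is adjusted for the number of flies still active. The fly variables recorded per visit (26.1.1) are number, sex and age.

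The 30% criterion is applied at time zero (13.1, 21.1.3.2). The persistence estimates, ET50 among them, guide the final choice of products for the field (13.1).

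**The concern.** Equation 1 measures repellency only if the flies available to land are the same in C and T. An insecticide on the arm may break that condition. A fly that touches treated fabric and is killed or knocked down adds nothing to T afterwards, and the formula cannot tell it from a fly that stayed away. If the same flies are used through the day, the shortfall carries into every later reading, so apparent protection can hold up or even rise while real repellency wanes.

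This differs from general fatigue or natural fly loss, which would affect every active. An insecticidal effect falls on one product and so biases the comparison between products. It also does not carry over to the field, where wild flies around a child are an open population that one device does not use up. At stake are permethrin's laboratory persistence, its rank against the other devices, and one field place.

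**Working it through.** **The plan's own figure.** The plan gives no figure on this point. The laboratory sample size does reproduce: (1.96 × 30/15)² = 15.37, rounded up to 16, and 17 after 5% loss. That number concerns precision and says nothing about this bias.

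**Step 1: what Equation 1 returns.** Let r be true repellency and m the fraction of fly activity lost to knockdown, with contact proportional to active flies. Then T = C(1 − r)(1 − m), so

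PE = 1 − (1 − r)(1 − m).

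With r = 0, PE equals m. With r = 20% and m = 30%, PE = 1 − 0.8 × 0.7 = 44%.

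**Step 2: build-up over the day.** Inputs from the documents: ten-minute readings, seven with the device on (time zero, then hours 1 to 6), and a single opening control. Assumptions: the same flies throughout, zero true repellency, no recovery, and a constant fraction q of active flies lost per reading. The documents give no value for q, so a range is shown. With h = −ln(1 − q), the mean active fraction during reading k is (1 − q)^k × q/h, so

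PE_k = 100 × [1 − (1 − q)^k × q/h].

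For q = 10%, q/h = 0.949. At hour 6, 0.9⁶ × 0.949 = 0.531 × 0.949 = 0.504, so PE = 49.6%.

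| Assumed loss per reading | PE at 0 h | PE at 3 h | PE at 6 h |
|---|---|---|---|
| 2% | 1% | 7% | 12% |
| 5% | 3% | 16% | 28% |
| 10% | 5% | 31% | 50% |
| 20% | 10% | 54% | 77% |

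**Step 3: ET50.** Equation 2 (26.3.3) regresses ln[p/(1 − p)] on time; for one device the dose term is constant. An unweighted fit to the seven values for q = 10% gives an intercept of −2.40 and a slope of +0.446 per hour. Solving for p = 0.5 gives 2.40/0.446 = 5.4 h. The slope has the wrong sign: the returned ET50 is when apparent protection rises through 50%, for a device with no repellency.

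**Step 4: the time-zero gate.** If a fraction K is lost during the first reading, PE = 1 − K/[−ln(1 − K)]. K = 0.53 gives 29.8% and K = 0.54 gives 30.5%. About 54% of flies would have to be disabled within the first ten minutes to reach 30% by loss alone.

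**Step 5: does a per-fly denominator help?** For q = 10% at hour 6, the active fraction is 0.9⁶ = 0.531 before the reading and 0.9⁷ = 0.478 after it, mean 0.505. Contact per active fly, relative to control, is 0.504/0.505 = 0.999, so PE is about 0.1% instead of 49.6%.

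**The case against.** Use of one batch of flies for six hours is inferred. The instruction "The participant will then re-insert his/her arm into the cage with the test insects" belongs to the topical dose series, which runs without delay between doses; 21.1.3.2 and 21.1.4 do not say whether the hourly readings use the same flies, and operating procedures may settle it. This stands as a limit. Renewing flies hourly would stop the build-up, though knockdown within each ten-minute reading would still count as protection. The device is also with the flies for only about 7 × 10 = 70 minutes, not six hours; the illustration already counts loss during readings only.

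A reader might infer that knockdown lets a useless device pass the 30% gate. The documents do not support this: the gate applies at time zero, before loss has accumulated, and step 4 shows how extreme the early loss would have to be.

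A reader might also infer that heavily depleted sessions would be thrown out under the closing-control rule in 21.1.3.1: "If at this point there are less than five fly contacts, the results of the experiment will be discarded". That rule follows the topical dose series and uses diluent on the other arm. Section 21.1.4 omits diluent before its control and summarises the device sequence as a control followed by tests, so it is not clear that the rule applies. If it does, it is a weak check: with 20 or 100 contacts at baseline (assumed), a loss of 1 − 5/20 = 75% or 1 − 5/100 = 95% would still pass. It never corrects PE.

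Finally, the consequences are bounded. Permethrin is optional (12.1), field PE informs Phase 3 (16.2.2), and the field trial has wild flies and a no-product group (13.2), so a false laboratory lead would be tested there. All of this stands.

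**Conclusion.** The point holds for the later hourly PE values and ET50 in the laboratory device tests. Equation 1 credits disabled flies as protection, one candidate is an insecticide, and nothing in the protocol counts or corrects for the loss. At hour 6 the assumed losses of 2% to 20% per reading correspond to a spurious PE of about 12% to 77%. These figures rest on the same flies serving all day, no recovery, a constant loss rate and zero repellency.

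It would go too far to say that permethrin's ET50 will be inflated. The documents give no knockdown rate for this fly and format, and the bias could be negligible. What they do show is that the plan could not detect or remove it. A fresh control each week also keeps the build-up within one test day, provided new flies are brought in. The cost of leaving it is a distorted laboratory ranking and possibly one of up to four field arms (29 children) given on the strength of an assay artefact. The field estimates themselves are not affected.

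**What to change.** In 21.1.4, state whether flies are renewed between readings. For every device, not only permethrin, count the flies unable to fly before and after each reading, including the control, and add these counts to the variables in 26.1.1. In 26.3.1, compute C and T per active fly (for example, total contact duration divided by the mean of the two active counts) for the hourly PE and for the PE values that enter Equation 2. Report knockdown as a separate result beside repellency. Counting for all devices also picks up ordinary fly loss.

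The cost is a fly count at each reading. No extra participants, visits or flies are needed.

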21.2 Field trials

21.2.1 Test insects and testing site

Participants will be exposed to fly-face (including eye, nose and mouth) contacts outside their house. Previous studies indicate that the majority of such contacts will be *Musca sorbens*, although *Musca domestica* may be present (46); data thus far from our field site corroborates this prediction. Ambient temperature and humidity will be recorded at every fly-face observation period. Testing will be started between 09:00 and 10:00, as preliminary data from the same locality indicate that *M. sorbens* are less active earlier in the day, allowing for the six-hour testing duration. Should the fly density at the time of year of testing be very high, the test durations may be shortened (e.g. to five minutes), as a robust measure of protection will be obtained in a shorter interval.

21.2.2 Pilot Phase

We will conduct an initial pilot study to refine and validate the proposed methodologies for Phase 2 Repellent Testing. The pilot study will focus on 10 households each with one child aged three to 12 years, on whom fly-eye observations will be conducted both before and after the application of diluent only. Semi-structured pilot acceptability interviews will be conducted, to help refine and revise the topic guides. The Pilot will further enable us to determine whether fly density in the area is appropriate to the study.

21.2.3 Topical repellents

Eligible **participants** will be randomly allocated in equal proportions to the study groups, as per section 13. The repellent products and product formulations to be tested will be determined before the study commences. Each study participant will test only one product type, to minimise participant discomfort. Participants will be advised not to apply any cosmetics associated with a strong scent, such as perfume, hand cream, body wash, or other scented products. Additionally, volunteers will be asked not to consume spicy foods, i.e. curries, chillies and garlic for the 12 hours prior to the tests. This will be verified with the participants prior to the commencement of any tests.

The participants face will first be washed with unscented soap then rinsed with water and towel dried. The participant will then be seated comfortably on a chair outside their house, facing the investigators (entomological field worker and nurse), and will be instructed to refrain from touching the face or brushing away landing flies. For the first test, the diluent alone (50 µL) will be tested as a control. This will be applied to the participant's face (cheeks) and allowed to dry for one minute. The participant's face will then be videoed for ten minutes by the investigator or field laboratory assistant. During this time period, fly behaviour will be manually recorded and scored. The video footage will retrospectively be analysed for (i) fly-eye (ii) fly-nose (iii) fly-mouth and (iv) fly-face contact. After this ten-minute period of control measurements, the pre-allocated topical repellent will be applied to a circular area on the participant's cheek by the Stronger-SAFE field

team nurses. Topical repellents will be applied in a 6 cm diameter circle on the cheek, at least 3 cm below the eye and positioned away from the nose and mouth. The repellent will be allowed to dry for one minute, then the videoing and observation will be repeated for another ten-minute period. Test measurements will then be repeated hourly for five further time points (Figure 7). After the final time point, the participant will be provided with soap and water to clean off the topical repellent.

[figure not shown]

Figure 7. Study design for estimation of personal protection by topical repellents from fly-eye and fly-face contacts by *Musca sorbens*. This process will be repeated for each of 29 participants.

21.2.4 Wearable repellent devices

Control measurements will be taken for a ten-minute period, exactly as with the topical repellent testing, but omitting the face washing step. After this, the pre-allocated wearable repellent device will immediately be administered. Field nurses will demonstrate how to wear the repellent device, which will then be given to the participant to wear, or his/her primary caregiver to put on to the participant. The participant will then be seated again, and the videoing and observation repeated for another ten-minute period, as with the topical repellent testing. Again, the ten-minute observation period will then be repeated hourly for five further time points. After the six-hour test period, the participant will be asked to continue to wear the repellent device. The investigators will return one week later to repeat test sampling, at which point they will measure for ten minutes with the wearable repellent device still in place, then remove the device and measure for a further (control) ten minutes (Figure 8).

[figure not shown]

Figure 8. Study design for estimation of personal protection by wearable repellent devices from fly-eye contacts by *Musca sorbens*. This process will be repeated for each of 29 participants.

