Relative to other vectors of disease, very little is known about the biology and ecology of *M. sorbens*, although limited studies are available (27, 28, 42–45). Particularly, the only *M. sorbens* control measures that have been robustly studied are that of insecticide, and breeding site/larval source management (46). However, other closely related species are better understood, and repellents have been used with mixed success against the bush fly *Musca vetustissima* (47, 48), the face fly *Musca autumnalis*, and the housefly *Musca domestica* (48–50). Insecticide-impregnated ear-tags have also been developed for use in cattle, against horn- and face-flies (51).

10 Research hypothesis

Commercially available insect repellent products can be used to decrease contact to the face, particularly the eyes, nose and mouth, by the eye-seeking fly *Musca sorbens*. The protection afforded by insect repellents will prevent transmission of *Chlamydia trachomatis* by infected flies, as well as reducing the nuisance caused by this species.

11 Choice of comparators

It is well-established that individuals vary in their attractiveness to biting insects. A number of factors are thought to contribute to this variation in attractiveness, including body weight and/or

surface area (52), hormones (53), genetic factors (54) or disease (55, 56). Although *Musca sorbens* flies do not imbibe a blood meal, they are attracted to the face, and this attraction is presumably mediated via cues including odour and vision, that are highly person-specific. Further, there is evidence to suggest that flies are more attracted to individuals with ocular or nasal discharge, which is in turn influenced by the presence of trachoma. It is therefore reasonable to speculate that for a multitude of reasons some individuals are more attractive to *M. sorbens* flies than others, and therefore a within-subject trial, which controls for such variation, is the optimal study design.

12 Study Objectives

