13.2 Field trial

In the field clinical trial, eligible participants will be randomised between groups (study arms), each of which will test only one topical repellent or slow-release wearable repellent device, at one concentration. A maximum of four groups will be tested in addition to a control group, and each group will contain 29 children between the ages of three and 12 years. The additional control group, receiving no product, will allow for temporal comparison of fly contact across a day of testing.

The combination of product and product format to be tested will be determined before the study commences. The PE will be determined by measuring the frequency of fly-eye, fly-nose, fly-mouth and fly-face contacts by *Musca sorbens* after application of the product, in a 'field' environment where these flies are naturally present at high density. Control measurements will be taken of fly contact on each participant prior to this. Test measures will be repeated over a period of six hours to determine the ET_{50} , and for wearable repellent devices, participants will continue to wear the

product and tests will be repeated at one, two, three and four weeks later. Topical repellents will be applied by the Stronger-SAFE field team nurses, who will also demonstrate how to wear the repellent devices. A qualitative assessment of acceptability and barriers to use will be carried out at the end of the trial.

14 Study setting and populations

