20.2 Field trials

Prior to approaching members of the communities in which we wish to work there will be initial dialogues with the community leaders and local health officials to introduce the purpose and nature of the research project. Following this, participants will be recruited by visiting households in the study site that are home to children in the correct age bracket. Information about the study will be shared with potential participants by members of the field research team, who have previous experience in the participant information and consenting processes. During the visit, participants will be provided with Information Sheets (Appendices 4 and 5), a Product Information Sheet (Appendix 6) and Informed Consent and Assent forms (Appendix 7). Assent will be sought from the participant, and consent from the primary caregiver. This will be in Afaan Oromo, the

regional language. This will be read to those who are unable read. After verbal explanation of the relevant sections of the Information Leaflet and having the opportunity to ask questions, informed consent will be gained and evidenced by a signature or thumbprint signature (deemed acceptable locally due to high rates of illiteracy), in the presence of the study team and independent witness.

Eligible participants will be randomised equally between the topical repellents and wearable repellent devices found to be protective in laboratory clinical trials, and a control group receiving no intervention.

21 Study procedures

This clinical trial encompasses a series of laboratory studies, designed to determine which of a number of commercially available repellents provide protection against laboratory-reared *Musca sorbens* fly contact, followed by a field trial testing the protection afforded by these repellents and wearable repellent devices, from fly contact by wild *M. sorbens* on children aged three to 12 years. In the field trials, the acceptability of these products to the end-users (both children and their caregivers) will be assessed.

Prior to both trials, preliminary benchmarking laboratory studies will be conducted to determine which of five repellent actives will be studied in the clinical trials.

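### Topical arms are washed before the control reading, wearable arms are not, and both share one no-product arm: one format is unmatched, and late topical PE and ET50 may be biased downward

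*Combined protocol and SAP*

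**What the plan says.** Section 21.2.3, topical arms: "The participants face will first be washed with unscented soap then rinsed with water and towel dried". Diluent is applied, a ten-minute control reading is taken, and the repellent follows. There is a test reading straight away and then five more at hourly intervals. No second wash or second control reading is described, and section 24.1 asks that the product not be washed off during the six hours.

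Section 21.2.4, wearable arms: the control reading is taken "exactly as with the topical repellent testing, but omitting the face washing step". Hourly readings follow as for topicals. The follow-up visit a week later adds a same-day control reading after the device is removed.

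Control arm: section 13.2 says "A maximum of four groups will be tested in addition to a control group" and gives its purpose: "The additional control group, receiving no product, will allow for temporal comparison of fly contact across a day of testing". Section 20.2 says "Eligible participants will be randomised equally between the topical repellents and wearable repellent devices found to be protective in laboratory clinical trials", together with "a control group receiving no intervention". Neither section says whether the control children are washed or receive diluent.

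Analysis: section 26.3.1 computes field PE within each child: "C is the frequency of fly-eye contacts before application of repellent ('control' measure), and" T is the same count after application. Equation 2 in section 26.3.3 fits ET50 to that PE. Section 19.2, by contrast, powers the field trial on product arm versus control arm.

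Section 11 states that "there is evidence to suggest that flies are more attracted to individuals with ocular or nasal discharge".

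**The concern.** Two separate problems follow from washing one format and not the other.

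1. **Unmatched control.** With one no-product arm prepared in one way, either the topical arms or the wearable arms differ from it in washing as well as in product. The contrast that sets the sample size then mixes the two for that format.

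2. **Drift in the topical arms.** The topical denominator is fixed just after a wash, and later readings are set against it for the rest of the day. If washing removes some of what attracts the fly and this returns, contacts rise for a reason unrelated to the repellent. That rise is counted as lost protection. Wearable arms have no such drift, so comparing effective times across products (section 12.2) would favour wearables.

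Section 16.2.2 says the field results decide which repellents go into the Phase 3 trial, so a tilt between formats matters.

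**Working it through.** **The plan's own figure.** Section 19.2 gives a difference of 30 points, SD 30% and power 90%. Alpha is not stated; two-sided 0.05 is assumed here. The normal formula gives 2 × (1.960 + 1.282)² × 30²/30² = 21.0, rounded up to 22. The two-sample t-test gives 22.02, rounded up to 23, which matches the plan. Then 23 × 1.25 = 28.75, or 29. At 23 per arm the t-test power is 91%.

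**Model for the wash (assumed).** Washing lowers contacts at the control reading by a fraction w, and a fraction r of that loss has returned by a later reading. For true PE p:

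- observed PE = 1 − (1 − p) × f
- f = (1 − w(1 − r)) / (1 − w)

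With full recovery (r = 1), f = 1/(1 − w). With no recovery (r = 0) or no effect (w = 0), f = 1 and there is no bias. The documents give neither w nor r, and no part of the plan, including the pilot in section 21.2.2, is described as measuring them.

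**Late PE in a washed topical arm, against its own control reading:**

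| w | true 50%, r = 0.5 | true 50%, r = 1 | true 30%, r = 0.5 | true 30%, r = 1 |
|---|---|---|---|---|
| 0 | 50% | 50% | 30% | 30% |
| 10% | 47.2% | 44.4% | 26.1% | 22.2% |
| 20% | 43.8% | 37.5% | 21.3% | 12.5% |
| 30% | 39.3% | 28.6% | 15.0% | 0% |

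Example: w = 20%, r = 1, true 50% gives 1 − 0.5/0.8 = 37.5%.

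**ET50.** Assume PE of 80% at time zero, a logit-linear decline with true ET50 of 4 h, and linear recovery from washing over 5 h. The observed ET50 is then 3.6, 3.2 or 2.9 h for w = 10%, 20% or 30%.

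**Product versus control, late reading, true PE 30%, r = 1, SD 30%, 23 per arm:**

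- Washed topical against unwashed control: the contrast is 22.2 points (power 69%) at w = 10% and 12.5 points (power 28%) at w = 20%. With r = 0.5 it is 26.1 points (82%) and 21.3 points (65%).
- Unwashed wearable against washed control: the control arm's own PE is 1 − f, which is −11.1% or −25.0%. The contrast is 30 + 11.1 = 41.1 points or 30 + 25.0 = 55.0 points.

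The two errors run in opposite directions.

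**Does a matched control remove the drift?** If product and no-product arms are both washed, T/C is (1 − p)f in the product arm and f in the no-product arm. The ratio is 1 − p for any w and r, so p is recovered. A plain difference of PEs gives p × f, for example 33.3 points at w = 10% and 37.5 points at w = 20% for true PE 30% and r = 1. The drift therefore cancels on the ratio scale and not exactly on the difference scale.

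**The case against.** A reader might infer that sharing one control arm is what distorts PE and ET50. The documents do not support that. The control arm appears in neither Equation 1 nor Equation 2, so its preparation cannot change those quantities as written. Any drift in them comes from the single wash before the topical control reading and would be present with two control arms. The unmatched control affects the section 19.2 contrast and the time-of-day comparison.

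A reader might also take it as documented that washing lowers fly contact. Section 11 says only that there is evidence flies prefer faces with discharge. That washing lowers contacts, and that this reverses within six hours, is inference. The most that can be said is that late topical results may be biased, and the 0% entry in the table needs both w = 30% and complete recovery.

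Three further limits stand:

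- At time zero the control and first test readings share the same wash status and are minutes apart, so early PE is little affected.
- The mismatch arises only if both formats are fielded; the arms depend on the laboratory results.
- It is not true that no control arrangement could match both formats. Splitting the control arm by preparation would do so; only one uniform preparation cannot.

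Section 26.1.2 does record ocular and nasal secretions, but no analysis is specified that uses them. What remains is a stated difference in procedure between randomised arms, not merely missing detail.

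**Conclusion.** The point holds in two parts of different certainty. If both formats are fielded with one uniformly prepared control arm, one format is compared with a control that differs in washing; this follows from the text. That late topical PE and ET50 are biased downward relative to wearables is conditional: washing must lower contacts and the effect must wear off. Over an assumed w of 0 to 30% with full recovery, a true late PE of 50% reads as 50% down to 29%. Partial recovery gives less bias and no recovery gives none. The power figures also assume two-sided 0.05, an unchanged SD of 30% and a contrast taken at a late reading; section 19.2 does not say which reading it means. This should be changed before the field trial, but it does not invalidate the time-zero results.

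**What to change.** - **Preparation.** Use the same face-wash step and the same waiting time before the control reading on the first test day in every field arm, including the no-product arm.
- **Analysis.** Supplement Equation 1 with a between-arm comparison of change from the control reading at each hour. Take it as the ratio of T/C in the product arm to T/C in the no-product arm, so that post-wash and time-of-day drift cancel. Base the ET50 comparison across products on the PE adjusted in this way.
- **Diluent.** Reconcile sections 20.2, 21.2.3 and 21.2.4. Read literally, section 21.2.4 drops only the wash and so keeps diluent in wearable arms, while the control arm is described as receiving no intervention. State which arms receive diluent.

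The cost is soap, water and a few minutes per child in the wearable and control arms, one added analysis, and a formal amendment under section 29.2. Washed faces are less natural and baseline contacts may be lower. Washing the wearable arms also gives their within-child PE the same possible drift, so the wash should not be equalised without the between-arm comparison.
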